Dated: 1/03/2024

Study Protocol/Synopsis

A Comparative Analysis of Hypocalcemia Incidence in Patients Undergoing Thyroidectomy: Ligasure vs Conventional Ligation of vessels by knot tying.

NCT Number: NCT06716632

A Comparative Analysis of Hypocalcemia Incidence in Patients Undergoing Thyroidectomy: Ligasure vs Conventional Ligation of vessels by knot tying.

Introduction:

Thyroidectomy is surgical removal of all or part of the thyroid gland, which is located in the front of the neck. Depending on how much thyroid tissue is removed, thyroidectomy could be classified into Total thyroidectomy, subtotal thyroidectomy, near total thyroidectomy and lobectomy.

In total thyroidectomy, the entire thyroid gland is removed. In thyroid lobectomy, one lobe of the thyroid gland is removed. In Thyroid lobectomy with isthmectomy, thyroid lobe along with the isthmus is removed. In Subtotal thyroidectomy, a small portion of the thyroid gland is left during the surgery. This portion is near the trachea, parathyroid glands and the recurrent laryngeal nerve. Indications for thyroidectomy are thyroid cancer, MNG, solitary thyroid nodule.

Complications of thyroidectomy include hoarseness or change in voice (33.3%), damage to parathyroid glands causing hypocalcaemia (54.4%), wound infection (3.4%), dysphagia (32.8%). Several risk factors may contribute to the occurrence of post-thyroidectomy complications, including age, gender, enlarged gland size, type of thyroid disease, presence of fibrosis and inflammation, extent of thyroidectomy, and lymph node dissection. Among these complications, hypocalcaemia and recurrent laryngeal nerve injury are the most frequently observed^{1,2}.

The superior and inferior parathyroid glands, located near the thyroid gland, play a vital role in calcium homeostasis by producing parathyroid hormone (PTH), which regulates calcium levels in the bloodstream.

Hypocalcemia, characterized by low serum calcium levels. It is a frequent and significant complication of thyroidectomy due to damage, ischemia, or removal of one or more of the parathyroid glands during surgery. It can be categorized into two main types, transient hypocalcemia and permanent hypocalcemia. The primary difference between these two types lies in the duration. Transient hypocalcemia lasts for 3 months after surgery, while permanent hypocalcemia persists for 3 months or longer after surgery³.

To minimize the risk of parathyroid gland damage, various surgical techniques have been developed, including the utilization of energy-based devices such as Ligasure. Ligasure has gained popularity in thyroidectomy procedures due to its potential advantages in terms of precision, hemostasis, and reduced operative time.

Ligasure is a bipolar vascular sealing system utilized to achieve effective control of bleeding and create a bloodless surgical environment. It operates by utilizing an electrical current within the frequency range of 2-4 MHz It induces denaturation of collagen and elastin within the vessels and surrounding tissues. The localized tissue temperatures typically range between 60-100°C, facilitating the fusion of collagen and elastin in the vessel walls. This fusion process creates a durable sealed zone without any carbonization and enables hemostasis in vessels with diameters of up to 7 mm^{4,5}.

Conventional methods of vessel ligation, which involve the use of ties and suture ligatures, have long been employed in most medical centers. While these techniques effectively control bleeding from vessels, they are time-consuming and carry the risk of harming adjacent structures like the recurrent and superior laryngeal nerves. In light of the growing demand for time-saving procedures, particularly in high-volume operating theaters where efficient patient turnover is essential, there is a growing interest in devices or techniques that minimize the reliance on conventional knot-tying or suture ligation for achieving hemostasis. This is particularly important to optimize anesthesia time and improve overall efficiency⁶.

According to a recent study, hypocalcemia occurred in 6.7% of individuals who underwent surgery using the Liga Sure method⁷. In a separate study, 32.4% of patients who had surgery utilizing the traditional knot tying technique experienced hypocalcemia⁸.

However, despite the increasing use of Ligasure and other energy devices, there is a paucity of research comparing their efficacy in preventing hypocalcemia after thyroidectomy. Therefore, this study aims to address the existing gap in knowledge by conducting a comprehensive comparison of the incidence of hypocalcemia in patients undergoing

thyroidectomy using Ligasure versus the conventional artery forceps/knot tying technique. **Objective**:

This study aims to address the existing gap in knowledge by conducting a comprehensive comparison of the incidence of hypocalcemia in patients undergoing thyroidectomy using Ligasure versus conventional ligation of vessels by knot tying. Additionally, secondary outcomes such as operative time, intraoperative bleeding, length of hospital stay, and postoperative complications will be assessed to provide a holistic understanding of the two surgical approaches.

Hypothesis:

The incidence of hypocalcemia in patients undergoing thyroidectomy using Ligasure is less versus conventional ligation of vessels by knot tying.

Operational definition:

1)Hypocalcemia: Patients having calcium level below 8.0 mg/dL will be labelled as hypocalcemia.

Material and methods:

1)Study design:

Randomized control trial

2)Study setting:

Surgical unit I Gulab Devi hospital, Lahore

3) Duration of study:

6 months after approval of study.

4)Sample size:

Sample size will be 76 patients (38 in each group) calculated by WHO calculator, with confidence interval of 95% and margin of error 5%, power of test at 90% taking 6.7 % in Liga Sure⁷ vs 32.4% in conventional knot tying technique⁸.

5)Sampling technique:

Non-probability purposive sampling for including patients in study and random allocation for grouping of patients using lottery method.

6)Sample Selection:

Inclusion criteria:

1) Patients from both genders.

2) Age between 20 years to 50 years.

3) Patients undergoing Total thyroidectomy for benign thyroid disease.

Exclusion criteria:

1) Patients having pre-operative hypocalcaemia.

2) Patients having malignant thyroid disease.

3)Patients having recurrent thyroid disease.

4)Patients having lobectomy + isthmectomy.

5)Patients having pro-operative calcium supplements.

Data collection procedure:

After approval from hospital ethical committee, 76 patients (38 in each case) will be enrolled presenting in department of Surgery, Gulab Devi Hospital, Lahore for total thyroidectomy. Informed consent will be taken from each patient. Demographic information including age and address will be noted. Patients will be divided into two groups by using lottery method.

Group A will be managed with Ligasure and group B will be managed with conventional ligation of vessels by knot tying. All the patients will be subjected to their treatment according to their respective groups by single experienced surgeon having minimum experience of five years. Calcium levels will be taken pre operatively, 24 and 48 hours postoperatively. All the data will be collected in a pre-designed proforma. All information regarding patients will be kept confidential and bias will be addressed by single blind data collection procedure.

Data Analysis:

Statistical analysis will be done using Statistical Package for Social Sciences (SPSS) version 24. Mean and standard deviation was calculated for all quantitative variables like age, BMI, serum calcium level. Qualitative data like gender, presence of hypocalcemia will be presented as frequencies and percentages. Chi square test will be applied to compare two treatments effectiveness by taking P value 0.05 as significant.

References:

4. Mishra V. Comparative study between harmonic scalpel and ligasure vessel sealing system: in open and laparoscopic surgery. World J Laparosc Surg. 2013;6(2):74-6.

7. Ahmed H. Khafagy a, Ibrahim Abdelnaby. Total thyroidectomy: Ligasure versus Clamp & Knot technique for intraoperative hemostasis. Egyptian Journal of Ear, Nose, Throat and Allied Sciences (2013) 14, 59–65.

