## STATISTICAL ANALYSIS PLAN

## A Comparative Analysis of Hypocalcemia Incidence in Patients Undergoing Thyroidectomy: Ligasure vs Conventional Ligation of vessels by knot tying.

**NCT Number:** NCT06716632

**Objectives:** To compare the incidence of postoperative hypocalcemia between LigaSure and conventional knot-tying techniques in total thyroidectomy patients.

**Methods**: A randomized controlled trial was conducted at the Surgical Department of Gulab Devi Hospital, Lahore, from July 2024 to January 2025. Seventy-six patients who underwent total thyroidectomy for benign thyroid disease were randomly allocated to the LigaSure (n=38) and conventional knot-tying (n=38) groups. Serum calcium levels were measured preoperatively and at 24/48 hours postoperatively. For statistical analysis, SPSS v24 was used and non-parametric tests like the Mann-Whitney U and chi-square tests were used.

**Results:** Differences found in operative time (p=0.106), intraoperative bleeding (p=0.867), hospital stay (p=0.967), or hypocalcemia incidence (LigaSure: 10.5% vs. Conventional: 7.9%; p=0.692) were of no significance.

**Conclusion:** Both techniques demonstrated comparable safety profiles with no statistically significant differences in postoperative outcomes. LigaSure offers a comparable alternative to conventional methods when used by experienced surgeons.

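### The stated 90% power is not that of the planned test: 38 per group gives about 82–85% with a two-sided chi-square test at 0.05, and sidedness is not stated

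*Protocol*

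**What the plan says.** Four statements bear on this point.

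- Protocol, Material and methods, item 4 (Sample size), for a total of 76: "38 in each group) calculated by WHO calculator, with confidence interval of 95% and margin of error 5%, power of test at 90" per cent. The rates are 6.7% for LigaSure and 32.4% for conventional knot tying. No formula and no sidedness are given.
- Protocol, Hypothesis: "The incidence of hypocalcemia in patients undergoing thyroidectomy using Ligasure is less versus conventional ligation of vessels by knot tying". This is worded in one direction.
- Protocol, Data Analysis: "Chi square test will be applied to compare two treatments effectiveness by taking P value 0.05 as significant". No one-sided rule and no continuity correction are mentioned.
- SAP, Results: "hypocalcemia incidence (LigaSure: 10.5% vs. Conventional: 7.9%; p=0.692) were of no significance".

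**The concern.** A Pearson chi-square statistic squares the difference between the groups, so a difference in either direction raises it. Comparing it with the 5% critical value is a two-sided test. A directional hypothesis does not change that unless the plan also says that only one direction counts and how the p-value is then obtained.

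The sample-size item should therefore give the power of a two-sided 5% test, and 38 per group looked too few for 90% at these rates. If so, the protocol understates the risk of missing the effect it was designed to find, and a reader cannot tell which test the calculation assumed. The wording adds to the difficulty: a margin of error belongs to estimating a single proportion, and here it appears to stand for the significance level.

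**Working it through.** **Inputs.** From the Sample size item: p1 = 0.067, p2 = 0.324, n = 38 per group, stated power 90%. From Data Analysis: chi-square test, α = 0.05. No dropout allowance is stated, so none is assumed.

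**Intermediate quantities**

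- Difference d = 0.324 − 0.067 = 0.257; mean rate p̄ = 0.1955
- Pooled: s0 = √(2 × 0.1955 × 0.8045) = √0.31456 = 0.5609
- Unpooled: s1 = √(0.067 × 0.933 + 0.324 × 0.676) = √0.28154 = 0.5306
- d√n = 0.257 × √38 = 1.5843

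**Trying to reproduce 38 per group for 90% power**

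Pooled formula: n = (zα·s0 + zβ·s1)² / d². Unpooled formula: n = (zα + zβ)²·s1² / d². For 90% power zβ = 1.2816.

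| α = 0.05 | Pooled | Unpooled |
|---|---|---|
| One-sided (zα = 1.6449) | 38.88, so 39 | 36.50, so 37 |
| Two-sided (zα = 1.9600) | 47.93, so 48 | 44.79, so 45 |

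The one-sided answers lie on either side of 38, but neither equals it. The two-sided answers are well above it. One further route does give 38: two-sided, 80% power (zβ = 0.8416), with the pooled variance used throughout, (1.9600 + 0.8416)² × 0.31456 / 0.257² = 37.38, rounded up to 38. That contradicts the stated 90%. The documents do not show which routine the calculator used, so the origin of 38 cannot be settled.

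**Power at 38 per group, two-sided 0.05**

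- Pooled: Φ[(1.5843 − 1.9600 × 0.5609) / 0.5306] = Φ(0.914) = 82.0%
- Unpooled: Φ(1.5843 / 0.5306 − 1.9600) = Φ(1.026) = 84.8%
- Exact: summing the two binomial distributions over every table in which the uncorrected Pearson test rejects gives 84.8%

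By the same exact method, power is 0.8936 at 43 per group and 0.9012 at 44, so 44 is the smallest number that reaches 90%.

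**Power at 38 per group, one-sided 0.05**

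- Pooled: Φ[(1.5843 − 1.6449 × 0.5609) / 0.5306] = Φ(1.247) = 89.4%
- Unpooled and exact: 91.0%

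**With a small-sample correction.** Exact two-sided power at 38 per group is 75.4% with the Yates correction and 77.4% with Fisher's exact test. The 82–85% range therefore assumes no correction.

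**Which test was reported.** 10.5% and 7.9% of 38 are 4 and 3 patients. Uncorrected Pearson χ² = 76 × (4 × 35 − 3 × 34)² / (7 × 69 × 38 × 38) = 0.157, two-sided p = 0.6916, which matches the SAP's 0.692. A one-sided p would be 0.654 in the hypothesised direction or 0.346 in the other. Yates and Fisher both give 1.0. The reported test was two-sided and uncorrected.

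**Effect on the result.** Difference (LigaSure minus conventional) = 4/38 − 3/38 = +2.6 points, standard error 6.6 points, Wald 95% CI −10.4 to +15.6. The assumed effect was −25.7 points, well outside this interval.

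**The case against.** The best defence is that the 90% is approximately right if the calculation was one-sided. The hypothesis is directional, sidedness is not stated, one-sided power at 38 is 89.4–91.0%, and this reading alters none of the stated parameters. The 80% route has to discard the one parameter the protocol states clearly. On that view the figure is unexplained rather than wrong, and writing a two-sided level into the protocol would record a choice it never made, inferred partly from a later p-value. It can also be said that 5–8 points of power matter little when the two rates come from separate studies, the observed conventional rate was 7.9% against an assumed 32.4%, and the trial has finished.

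Much of this stands. A one-sided calculation is a plausible origin and is the more natural of the two candidates. The correction changes no result. The 82–85% range does depend on using no continuity correction.

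It does not rescue the stated power. If the calculation was one-sided, the trial was sized for one test while another was planned and reported, which is the discrepancy at issue. Nor does the two-sided reading depend on the later p-value: it follows from how a chi-square test at 0.05 works, and the p-value only confirms it.

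**Conclusion.** The concern holds. For the planned test, power at 38 per group is 82.0% (pooled normal) to 84.8% (exact), which is 5–8 percentage points below the stated 90%. The corresponding false-negative risk is 15–18% rather than 10%. Reaching 90% would need 44 (exact), 45 (unpooled) or 48 (pooled) per group, that is 88 to 96 patients against the planned 76.

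This rests on the protocol's own rates, equal groups, no dropout, a two-sided 5% level and no continuity correction. A corrected or Fisher test would make the shortfall larger.

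It is an error in a stated design figure and should be corrected. It does not alter the trial's finding on hypocalcaemia.

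**What to change.** Keep 76 patients and replace the power statement in the Sample size item, marked as a correction:

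> *With 38 patients per group, a two-sided chi-square test without continuity correction at the 5% significance level has about 82% power (85% by exact calculation) to detect 6.7% versus 32.4%.*

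Replace the margin of error of 5% with a two-sided significance level of 5%, and state in Data Analysis that the chi-square test is two-sided and uncorrected. If the original calculator settings are on file, add the formula and sidedness actually used. The sentence above is true whatever they were.

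The cost is a sentence or two of text and a less favourable stated power. No patients are added, and no analysis or result changes.

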## STATISTICAL ANALYSIS PLAN

## A Comparative Analysis of Hypocalcemia Incidence in Patients Undergoing Thyroidectomy: Ligasure vs Conventional Ligation of vessels by knot tying.

**NCT Number:** NCT06716632

**Objectives:** To compare the incidence of postoperative hypocalcemia between LigaSure and conventional knot-tying techniques in total thyroidectomy patients.

**Methods**: A randomized controlled trial was conducted at the Surgical Department of Gulab Devi Hospital, Lahore, from July 2024 to January 2025. Seventy-six patients who underwent total thyroidectomy for benign thyroid disease were randomly allocated to the LigaSure (n=38) and conventional knot-tying (n=38) groups. Serum calcium levels were measured preoperatively and at 24/48 hours postoperatively. For statistical analysis, SPSS v24 was used and non-parametric tests like the Mann-Whitney U and chi-square tests were used.

**Results:** Differences found in operative time (p=0.106), intraoperative bleeding (p=0.867), hospital stay (p=0.967), or hypocalcemia incidence (LigaSure: 10.5% vs. Conventional: 7.9%; p=0.692) were of no significance.

**Conclusion:** Both techniques demonstrated comparable safety profiles with no statistically significant differences in postoperative outcomes. LigaSure offers a comparable alternative to conventional methods when used by experienced surgeons.

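### Operative time, a motivating secondary outcome recorded in minutes, is reported only as p=0.106 with no direction, difference or interval, yet the SAP concludes that the techniques are comparable

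*SAP*

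**What the plan says.** The protocol's Introduction credits LigaSure with "potential advantages in terms of precision, hemostasis, and reduced operative time" and goes on to argue from theatre efficiency: "In light of the growing demand for time-saving procedures, particularly in high-volume operating theaters where efficient patient turnover is essential". Its Objective section says that "secondary outcomes such as operative time, intraoperative bleeding, length of hospital stay, and postoperative complications will be assessed". Item 7 of the data form records operative time in minutes for each patient.

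The protocol's Data Analysis section covers continuous data by description only: "Mean and standard deviation was calculated for all quantitative variables like age, BMI, serum calcium level". The one between-group test it names is for proportions: "Chi square test will be applied to compare two treatments effectiveness by taking P value 0.05 as significant". It plans no test, difference or interval for a continuous outcome.

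The SAP's Methods section says that "non-parametric tests like the Mann-Whitney U and chi-square tests were used", without saying which test belongs to which outcome. Its Results section gives hypocalcaemia as a percentage per arm with a p-value. For the continuous outcomes it gives p-values alone: "Differences found in operative time (p=0.106), intraoperative bleeding (p=0.867), hospital stay (p=0.967". The Conclusion describes the techniques as comparable.

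**The concern.** A bare p-value says neither which arm was faster nor by how much. The protocol's efficiency argument turns on minutes per case, so a reader who wants to know whether LigaSure shortens the operation, lengthens it or makes no difference learns nothing from the SAP on that point.

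The conclusion of comparability needs more than a non-significant test. It needs an interval narrow enough to rule out differences that would matter. The trial was sized on hypocalcaemia (6.7% against 32.4%), and neither document gives an SD, a target difference or a power figure for operative time. Absence of significance at this sample size could hide a difference large enough to affect a theatre list, in either direction.

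**Working it through.** **Inputs.** From the SAP Results: p=0.106 for operative time; 10.5% against 7.9% with p=0.692 for hypocalcaemia. From the SAP Methods and the protocol's sample size section: 38 per arm. Assumed: the test is a two-sided Mann-Whitney, because the other test named does not suit minutes; times are roughly normal with a common SD; the SD is 15 to 30 minutes. No mean, median, SD or direction for operative time appears in either document.

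**Reported figure reproduced.** 10.5% and 7.9% of 38 are 4/38 and 3/38. An uncorrected chi-square test on these counts gives p=0.6916, which matches the reported 0.692. This supports 38 per arm as the analysed number. No figure for operative time other than its p-value is available to reproduce.

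**Step 1: p-value to z.** |z| = Φ⁻¹(1 − 0.106/2) = Φ⁻¹(0.947) = 1.62.

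**Step 2: rank scale.** The null standard error of the Mann-Whitney probability is √[(n₁+n₂+1)/(12·n₁·n₂)] = √[77/(12×1444)] = 0.0667. The probability that a patient in the slower arm took longer than one in the other is 0.5 + 1.616×0.0667 = 0.608. The half-width is 1.96×0.0667 = 0.131, so the 95% CI is about 0.48 to 0.74.

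**Step 3: SD scale.** Under a normal shift, the standard error in SD units is √(2/38)/√(3/π) = 0.2294/0.9772 = 0.235.
- Shift: 1.616×0.235 = 0.38 SD
- Half-width: 1.96×0.235 = 0.46 SD
- 95% CI: about −0.08 to 0.84 SD

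If the p-value came from a comparison of means instead, the factor √(3/π) drops out and the result is 0.37 SD (−0.08 to 0.82). The answer hardly depends on which test was used.

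**Step 4: minutes, for assumed SDs.** Positive values mean longer in whichever arm was slower.

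| Assumed SD (min) | Shift (min) | 95% CI (min) |
|---|---|---|
| 15 | 0.38×15 ≈ 6 | −1 to 13 |
| 20 | 0.38×20 ≈ 8 | −2 to 17 |
| 30 | 0.38×30 ≈ 11 | −2 to 25 |

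**Step 5: what 38 per arm could detect.** For 80% power at two-sided 0.05, the Mann-Whitney test needs a shift of (1.96+0.84)×0.235 = 0.66 SD. That is about 10 minutes at SD 15 (0.66×15) and about 20 at SD 30 (0.66×30).

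Under the same assumptions the half-width of about 0.46 SD applies to bleeding and hospital stay too. Their large p-values place the estimates near zero but do not make the intervals narrow.

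**The case against.** The strongest reply is that the gap lies in reporting, not in the trial, and much of that stands.

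- **A reader might infer that the trial cannot say how many minutes are saved or lost.** The documents do not support this. Minutes are recorded for each patient, and the protocol plans mean and SD for all quantitative variables. Two means and two SDs with 38 per arm give the difference and its Welch interval.
- **A reader might infer that the mean and SD summary contradicts the rank test.** It does not. One is a description and the other a test, and a rank test is a defensible choice for times and blood loss that may be skewed.
- **The Mann-Whitney test for this outcome is inferred.** That is true, and the point above is worded accordingly. Step 3 shows the size is nearly the same either way.
- **Operative time is secondary, and one of three advantages named.** This is also true. The hypothesis and the SAP objective concern hypocalcaemia, and no target in minutes is set. That limits the weight of the point but does not remove it.
- **Operative time has the smallest of the four p-values, and its interval includes no difference.** Correct: the calculation is not evidence of an effect, and the direction is unknown.
- **Any new analysis is post hoc.** This stands, and it argues against a covariate-adjusted model. Neither document plans adjustment, and the form shows no categories for pre-operative diagnosis, so the coding would be chosen after the results were known.

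What the reply does not answer is that the SAP concludes comparability while giving no estimate for these outcomes.

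**Conclusion.** The point holds as one of missing estimation. The SAP gives operative time as p=0.106 and nothing more, and that result is compatible with no difference or with one of up to about 0.84 SD. At an assumed SD of 15 to 30 minutes the upper limit is about 13 to 25 minutes. A conclusion of comparable operative times is therefore not supported by what is reported.

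The figures rest on a two-sided test, 38 analysed per arm, roughly normal times with equal spread and, for the minutes only, the assumed SD.

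A reader might go further and infer that LigaSure saves time and that the benefit has been overlooked. The documents do not support that: no direction is given, so the shift could equally favour knot tying. The change should be made, but it does not affect the primary comparison of hypocalcaemia.

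**What to change.** 1. State in the SAP which test was used for each continuous outcome.
2. Report operative time per arm as mean (SD) and median (IQR).
3. Report the unadjusted difference in mean minutes, LigaSure minus conventional, with a Welch 95% CI. Keep the Mann-Whitney test as a sensitivity check.
4. For bleeding and hospital stay, give the mean difference or the Hodges-Lehmann shift, with a 95% CI, in the recorded units.
5. Label these estimates as added after results were known. Leave out a covariate-adjusted model, or label it exploratory.
6. Limit any statement of comparability to what the intervals exclude.

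The cost is a re-run in SPSS on data already collected and a few sentences in the SAP. The downsides are the post-hoc label and the mean's sensitivity to outlying times, which the medians and the rank test guard against. The interval will not be narrow: its half-width for operative time should be about 1.96×√(2/38) = 0.45 SD, or roughly 7 to 13 minutes at an SD of 15 to 30 (0.45×15 and 0.45×30). Showing that width is the purpose of the change.

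### The conventional-arm event rate was 7.9% against a planned 32.4%, so the stated 90% power does not carry over to the result and p=0.692 cannot support a conclusion of comparability

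*SAP*

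**What the plan says.** The protocol's Hypothesis section is directional: "The incidence of hypocalcemia in patients undergoing thyroidectomy using Ligasure is less versus conventional ligation of vessels by knot tying". Its Sample size section says "Sample size will be 76 patients (38 in each group) calculated by WHO calculator", with "power of test at 90% taking 6.7 % in Liga Sure" and "32.4% in conventional knot tying technique". The Data Analysis section says "Chi square test will be applied to compare two treatments effectiveness by taking P value 0.05 as significant". It does not state whether the test is one- or two-sided, or which version of the chi-square is meant.

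The SAP file is written as a results abstract. It gives 38 patients in each group and reports "hypocalcemia incidence (LigaSure: 10.5% vs. Conventional: 7.9%; p=0.692) were of no significance". Its Conclusion then describes the two safety profiles as comparable and LigaSure as a comparable alternative in experienced hands. It gives no event counts and no interval, and does not compare the observed conventional rate with the planning rate. Neither document defines a margin for equivalence or non-inferiority.

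**The concern.** The sample size rests on many events under knot tying, about 12 in 38. The reported 7.9% means 3. With so few events the trial is far less able to detect a relative reduction than the protocol's power statement implies. A reader who puts the planned 90% power beside a non-significant p-value will take the null as strong evidence, and the Conclusion invites this by moving from non-significance to comparability. What is at stake is how the primary result is read: as a demonstration that the techniques are alike, or as a small comparison that showed no benefit and left a wide range of differences open.

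**Working it through.** **Inputs.** Planned rates 6.7% and 32.4%, 38 per arm, 90% power (Protocol, Sample size). Test: chi-square at 0.05 (Protocol, Data Analysis). Observed: 10.5% and 7.9%, 38 per arm, p=0.692 (SAP, Methods and Results). The only counts out of 38 that fit these percentages are 4 (4/38 = 10.5%) and 3 (3/38 = 7.9%).

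**1. The planned sample size.** At 90% power and 5% alpha, a one-sided calculation gives 39 per arm (pooled variance) or 37 (unpooled), close to the stated 38. Two-sided gives 48 or 45. By normal approximation, power at 38 per arm and the planned rates is 89% one-sided and 82% two-sided. The stated 90% therefore reproduces only as a one-sided figure.

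**2. The reported p-value.** Uncorrected Pearson chi-square, X² = N(ad − bc)² / (product of the four margins), for 4/38 vs 3/38:

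- ad − bc = 4×35 − 34×3 = 38
- X² = 76×38² / (38×38×7×69) = 0.157, two-sided p = 0.692

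This matches. The Yates and Fisher versions both give p = 1.0, so the reported test is consistent with a two-sided Pearson chi-square.

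**3. The gap in the conventional rate.**

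- Expected conventional events: 38 × 0.324 = 12.3; observed: 3
- Exact (Clopper-Pearson) 95% interval for 3/38: 1.7% to 21.4%
- P(3 or fewer of 38 | 32.4%) = 0.0004

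**4. Power for the planned relative reduction.** Planned risk ratio = 0.067/0.324 = 0.207. Power comes from summing binomial probabilities over all tables with two-sided Pearson p < 0.05 in LigaSure's favour, 38 per arm:

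| True conventional rate | LigaSure rate at RR 0.207 | Power |
|---|---|---|
| 32.4% (planned) | 6.7% | 85% |
| 21.4% (upper limit) | 4.4% | 65.5% |
| 7.9% (observed) | 1.6% | 22% |
| 2.0% (near lower limit) | 0.4% | 0.6% |

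If the true conventional rate were 7.9% and LigaSure abolished hypocalcaemia, power would be 35%.

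**5. Best possible LigaSure result given 3 conventional events.** For 0/38 vs 3/38, X² = 76×(38×3)² / (38×38×3×73) = 3.12. The p-value depends on the test:

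| Test | p, 0/38 vs 3/38 |
|---|---|
| Pearson, two-sided (reproduces the reported p) | 0.077 |
| Yates | 0.239 |
| Fisher, two-sided | 0.240 |
| Fisher, one-sided | 0.120 |
| Pearson, one-sided | 0.039 |
| Likelihood-ratio chi-square | 0.039 |

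With one more conventional event, 0/38 vs 4/38 gives two-sided Pearson p = 0.040.

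**6. What the data say about the effect.** Difference, LigaSure minus conventional: 4/38 − 3/38 = +2.6 points. The Wilson limits are 4.2% to 24.1% for 4/38 and 2.7% to 20.8% for 3/38. Newcombe interval:

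- lower: 0.0263 − √[(0.1053 − 0.0417)² + (0.2080 − 0.0789)²] = −11.8 points
- upper: 0.0263 + √[(0.2413 − 0.1053)² + (0.0789 − 0.0272)²] = +17.2 points

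The planned difference, 6.7 − 32.4 = −25.7 points, lies outside. The risk ratio is 4/3 = 1.33. The standard error of its log is √(1/4 − 1/38 + 1/3 − 1/38) = 0.728, so the approximate 95% interval is 0.32 to 5.6, which excludes the planned 0.207.

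**The case against.** A reader might infer that the trial could not have reached p < 0.05 whatever happened under LigaSure, and so did not test its hypothesis. The documents do not support this, for three reasons.

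First, the zero-event result depends on the test. The protocol names neither sidedness nor version, its hypothesis is directional, and its sample size reproduces at 90% power only one-sided. One-sided Pearson and the likelihood-ratio chi-square both give p = 0.039 for 0/38 vs 3/38. The statement holds for the two-sided Pearson test that matches the reported p, and must be tied to it.

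Second, three conventional events is an outcome, not a design constant. At a true rate of 7.9%, four or more occur 35% of the time, and 0/38 vs 4/38 is significant. That is low power, not inability.

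Third, the planned test was run on the planned numbers, the estimate points against LigaSure, and the intervals exclude the planned effect on both scales. One caution remains: a 25.7-point reduction is arithmetically impossible from a 7.9% baseline, so excluding it partly reflects the low conventional rate. The risk-ratio interval does not have that limitation, but it is a large-sample approximation on sparse counts.

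It is also fair to say that a failed planning rate is not in itself an error in the plan, and that power computed at an observed rate is a weak summary once data exist. The 22% comes from an imprecisely known rate and becomes about 38% one-sided. The interval for the difference should therefore carry the message. None of this rescues the comparability conclusion, which has neither an interval nor a margin behind it.

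**Conclusion.** The point stands as one of disclosure and interpretation. The conventional rate was about a quarter of the planning value, too large a gap to put down to chance under the assumed 32.4%. Two-sided power for the planned relative reduction is about 22% at a true conventional rate of 7.9% and 65.5% at the upper limit of its interval, so the stated 90% does not describe the trial as it turned out. The result shows no reduction with LigaSure and is inconsistent with the planned effect. With an interval from about 12 points fewer to 17 points more, it does not establish that the techniques are comparable.

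This rests on the counts 4 and 3, inferred from the percentages and confirmed by the reported p, and on a two-sided uncorrected Pearson test, inferred in the same way. Nothing here says that the reported p-value is wrong.

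**What to change.** In the SAP's Results, report hypocalcaemia as 4/38 (LigaSure) and 3/38 (conventional), a difference of +2.6 points (Newcombe 95% CI −11.8 to +17.2), and state that the conventional rate was 7.9% (exact 95% CI 1.7% to 21.4%) against 32.4% assumed. Name the test as a two-sided Pearson chi-square, once confirmed.

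In the Conclusion, replace both comparability statements with text such as: *No reduction in hypocalcaemia with LigaSure was shown, and the planned 25.7-point reduction is excluded. Because the conventional-arm rate was far below the planning value, the interval remains compatible with meaningful benefit or harm, and the stated 90% power does not apply at the observed rate.*

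Any remark about what zero LigaSure events would have shown must name the two-sided Pearson test. Power at the observed rate is optional and should not stand in for the interval.

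The cost is a few sentences, with no new data or patients. The stated power and the conclusion become less favourable.
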